The incidence of TEAEs in the SMQ hemorrhages was similar during treatment with pacritinib (33.7%) and BAT (30.4%) in the PERSIST-1/-2 studies. However, the incidence of hemorrhage events was lower in the 400 mg QD arm compared to the 200 mg BID arm for all categories of TEAEs, including SAEs. The most common bleeding events were epistaxis, contusion, hematoma and GI hemorrhage and these events occurred at a similar frequency to patients treated with BAT. Importantly, one of the most common TEAEs in the "watch and wait only" patients was epistaxis (26.3%), indicating a baseline level of bleeding without any therapy, in this MF population. Most events in the SMQ hemorrhages were low grade, however, severe and sometimes life-threatening and fatal hemorrhagic events have been reported across the PERSIST-1/-2 studies. These outcomes comprised predominantly GI bleeding (including gastric variceal hemorrhage, melena, and esophageal hemorrhage) and intracranial hemorrhage, cerebral hemorrhage and meningorrhagia. Overall, hemorrhagic TEAEs resulted in death in seven patients in the PERSIST-1/-2 studies, two treated with pacritinib 200 mg BID, four treated with pacritinib 400 mg QD, and one after crossover from BAT to pacritinib.

The incidence of a new hemorrhage event TEAE was highest at the start of treatment and then diminished with continued treatment in all treatment groups. Serious hematological events occurred in patients with complicated medical histories, severe comorbidities, concomitant antiplatelet use, and myelosuppression. The risk of bleeding episodes did not appear to be related to the degree of thrombocytopenia.

Diarrhea

Patients in the PERSIST-1/-2 studies were evaluated at baseline to assess usual bowel habits and instructed on the need for early intervention for possible GI adverse effects associated with treatment. During each study, standard supportive care measures were provided to control symptoms of GI toxicity.

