The incidence of the TEAE of diarrhea was higher during treatment with pacritinib (61.4%) than with BAT (14.2%) in the PERSIST-1/-2 studies. However, the incidence of diarrhea was generally lower in the pacritinib 200 mg BID arm than in the 400 mg QD arm for most categories of TEAEs. This was true for all TEAEs (48.1% vs. 65.7%, respectively), related TEAEs (48.1% vs. 60.2%), grade 3/4 TEAEs (3.8% vs. 6.5%), TEAEs leading to discontinuation (0% vs. 2.5%), and TEAEs leading to dose reduction (0.9% vs. 4.0%). However, the incidence of diarrhea reported as SAEs was similar in both the 200 mg BID and 400 mg QD arms (1.2% vs. 1.9%).

The incidence of diarrhea was highest in the pacritinib groups at the start of treatment and then diminished with continued treatment: 54.3% of patients in the 400 mg QD arm and 40.6% of patients in the 200 mg BID arm reported a new TEAE of diarrhea during the first eight weeks of treatment. Between Weeks 8 and 16, this had decreased to 10.9% of the 400 mg QD arm and 15.3% of the 200 mg BID arm. After Week 16, the incidence was <10% in either arm.

While patients in both pacritinib and BAT treatment arms experienced the onset of diarrhea within the first four weeks, overall the time to onset of the first episode of diarrhea was earlier for patients treated with pacritinib than BAT. Within the pacritinib treatment arms, the 200 mg BID arm was more likely to remain event-free both in the first eight to 12 weeks and over the duration of treatment compared to the 400 mg QD arm. Similar results were seen for the time course of grade 3/4 diarrhea.

Nausea and Vomiting

The incidence of the TEAE of nausea was higher during treatment with pacritinib (32.8%) than with BAT (8.3%) in the PERSIST-1/-2 studies. However, the incidence of nausea was lower in the pacritinib 200 mg BID arm compared to the 400 mg QD arm for related TEAEs (20.8% vs. 29.0%) and those TEAEs leading to dose reduction (0.9% vs. 1.9%). Very few patients in any group reported grade 3/4 TEAEs or SAEs of nausea or nausea AEs leading to discontinuation or dose reduction, and almost all of these were in the 400 mg QD arm.

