11.6 Safety Analysis

The assessment of safety will be based mainly on the frequency of AEs and the number of laboratory values that fall outside of predetermined ranges.

Treatment-emergent AEs will be coded using MedDRA and summarized by system organ class, preferred term, and treatment arm as the number and percentage of patients with an event. AE data for hemorrhagic and cardiac events will be identified based on SMQs and analyzed as a SMQ group by treatment arm. Incidences of hemorrhagic and cardiac AE data by SMQs over 8-week interval will be summarized by treatment arm. The following subsets of treatment-emergent AEs will also be summarized by treatment arm: AEs related to study treatment, CTCAE grade 3 or 4 AEs, AEs leading to treatment discontinuation, deaths, and SAEs.

Clinical laboratory data will be summarized with descriptive statistics by treatment and timepoint. Each patient's data will be classified by the CTCAE grade, where possible, and summarized in shift tables comparing the worst post-baseline visit to baseline.

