1. SCOPE

This document describes the statistical analyses and data presentations to be performed for protocol PAC203, “An Open-Label, Randomized, Phase 2 Dose-Finding Study of Pacritinib in Patients with Primary Myelofibrosis, Post-Polycythemia Vera Myelofibrosis, or Post-Essential Thrombocythemia Myelofibrosis Previously Treated with Ruxolitinib”.

This statistical analysis plan (SAP) provides a detailed description of the strategy, rationale, and statistical techniques to be used to determine the most appropriate dosage of pacritinib for future studies. It provides additional details concerning the statistical analyses that were mentioned in the protocol. If additional analyses are required to supplement the planned analyses described in this SAP, they will be identified as post hoc in the clinical study report.

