13.1 ADVERSE EVENTS

Treatment-emergent AEs (TEAEs) will be summarized by presenting, for each treatment arm, the count and percentage of patients having any TEAE, having a TEAE in each body system, and having an individual event according to version 16.0 of the MedDRA dictionary. CTCAE (version 4.03) grades and relationship to study medication will be summarized as appropriate. For summaries by CTCAE grade or relatedness, only the highest CTCAE grade or degree of relatedness of each SOC and/or preferred term will be summarized. A patient having the same event more than once will be counted only once and by greatest severity or closest relationship.

In addition, serious TEAEs (SAEs), CTCAE grade 3 or 4 TEAEs, TEAEs leading to study medication discontinuation, interruption, or dose reduction, TEAEs with an outcome of death, and related TEAEs will be summarized. A listing of all SAEs will be generated. The preferred term of TEAEs of all grades, as well as for TEAEs of grade 3 or 4 will also be presented for each treatment arm by decreasing frequency in the PAC 200 mg BID arm.

Cardiac, hemorrhage, skin neoplasms, and hypersensitivity TEAEs as defined by Standardised MedDRA Queries (SMQs) will also be summarized by SOC and preferred term. Cardiac TEAEs are all the preferred terms in the SMQs of Cardiac Arrhythmias, Cardiac Failure, Ischaemic Heart Disease, and Embolic and Thrombotic Events. Hemorrhage TEAEs are all preferred terms in the SMQ of Haemorrhages. Skin neoplasm TEAEs are all preferred terms in the SMQ of Skin Neoplasms (malignant and unspecified). Hypersensitivity TEAEs are all preferred terms in the SMQ

of Hypersensitivity. A listing of time to onset and resolution of these TEAEs will also be presented by treatment arm. These will also be presented graphically.

The counts and percentages for the causes of all deaths will be presented by treatment arm. A listing of all deaths, both on and off treatment, will also be generated. On treatment deaths are defined as deaths that occur on treatment and within 30 days of treatment discontinuation.

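### SAP 13.1 omits, without explanation, the 8-week-interval incidence of hemorrhagic and cardiac events by arm that Protocol 11.6 specifies, so no incidence over patients at risk is planned for them

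*Protocol*

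**What the plan says.** Protocol 11.6 (Safety Analysis) says that hemorrhagic and cardiac events will be identified by SMQ and analysed by arm, and adds: "Incidences of hemorrhagic and cardiac AE data by SMQs over 8-week interval will be summarized by treatment arm". It attaches no condition.

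SAP 13.1 (Adverse Events) covers the same events. Cardiac and hemorrhage "TEAEs as defined by Standardised MedDRA Queries (SMQs) will also be summarized by SOC and preferred term". On timing it says: "A listing of time to onset and resolution of these TEAEs will also be presented by treatment arm. These will also be presented graphically". No 8-week or other interval appears in SAP 13 or 13.1, and no exposure-adjusted rate is given.

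The SAP's modification table records several exclusions (PK/PD analyses, per-protocol population, GEE analysis of symptom score, interim analysis). It neither lists nor explains the absence of the interval summary.

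On the time pattern, Protocol 1.3.4 reports for the two earlier phase 3 trials: "The incidence of a new hemorrhage event TEAE was highest at the start of treatment and then diminished with continued treatment". The sentence goes on to say that this was so in every treatment group. For cardiac events the same section reports no clear pattern of onset.

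**The concern.** Cardiac and hemorrhage events are two of the four components of the primary safety measure for dosage selection (Protocol 11.1, SAP 13). They are also the IDMC's stated focus and the trigger for suspending enrollment (Protocol 2.2, 11.9). For these events the interval table is the only analysis in either document that would give incidence by period on treatment.

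Without it, the arms are compared on the crude percentage of patients with an event at any time. Those percentages can cover unequal follow-up:

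- Treatment-emergent events are counted to 30 days after the last dose (SAP 11.1), with no Week 24 cut-off. Before Amendment 6, treatment could continue past Week 24.
- Under several rules in Protocol 6.5, a patient on a higher dosage steps down and stays on drug, while a patient at 100 mg QD must stop for the same event. The safety population is analysed by the treatment initially taken (SAP 5.2), so time after a step-down counts towards the higher-dosage arm.

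A dosage comparison can therefore be moved by length of observation as well as by risk.

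**Working it through.** **1. Text comparison.** There is no stated figure to reproduce; the finding rests on setting the two documents side by side.

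| Element | Protocol 11.6 | SAP 13.1 |
|---|---|---|
| Events | Hemorrhagic and cardiac, by SMQ | Same |
| By arm | Yes | Yes |
| Incidence by 8-week interval | Yes | Absent |
| Onset timing | Through the interval table | Listing and graph |
| At-risk denominator | Not stated | None stated |

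**2. What unequal follow-up can do to a crude percentage.** The documents give no per-interval rates for these events, so the risks are assumed. Let p be the risk of a first event per 8-week interval, the same in both arms. Cumulative risk after k intervals is 1 − (1 − p)^k.

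| Assumed p | 16 weeks (k = 2) | 24 weeks (k = 3) |
|---|---|---|
| 1% | 1 − 0.99² = 2.0% | 1 − 0.99³ = 3.0% |
| 3.39% | 1 − 0.9661² = 6.7% | 1 − 0.9661³ = 9.8% |
| 8% | 1 − 0.92² = 15.4% | 1 − 0.92³ = 22.1% |

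At equal risk, the longer-followed arm shows about 1.4 to 1.5 times the crude percentage. Having every patient in one arm stop at Week 16 is an extreme case; real differences in follow-up would be smaller and their direction is not known in advance.

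**3. What a whole-period percentage cannot show.** Also on assumed rates: a front-loaded arm with 8%, 1% and 1% in successive intervals reaches 1 − 0.92 × 0.99² = 9.83%. A flat arm at 3.39% per interval reaches 1 − 0.9661³ = 9.83%. The totals agree while first-interval risk is 8% against 3.4%.

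**4. How precise the table would be.** Inputs: 50 patients per arm (Protocol 11.7) and 33.7% with any hemorrhage event (the pooled pacritinib rate in Protocol 1.3.4), so 50 × 0.337 ≈ 17 patients. Two splits of first events over Weeks 0–8, 8–16 and 16–24 are assumed, with all 50 in each denominator and exact 95% limits.

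- 60/25/15%: 10, 4 and 3 patients, with intervals 10.0–33.7%, 2.2–19.2% and 1.3–16.5%.
- Even split: about 6 patients per interval, each 4.5–24.3%.

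With only event-free patients in the denominator and no other losses, the last two entries of the first split become 4/40 = 10.0% (2.8–23.7%) and 3/36 = 8.3% (1.8–22.5%). The table is descriptive and imprecise, and grade ≥3 counts would be smaller still.

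**The case against.** The strongest reply is that this is a missing cross-reference. The protocol text still stands, its Section 11 is itself titled a statistical analysis plan, and SAP 1 says the SAP adds detail to analyses named in the protocol. The onset listing and graph cover exactly these events, and interval counts could be derived from them. SAP 9 reports treatment duration by arm, so unequal exposure would be noticed. The primary safety measure has no time component. The counts are small: at 50 per arm, the assumed 8% against 3.4% in the first interval is about 4 patients against 2, with exact limits of 2.2–19.2% and 0.5–13.7%.

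Much of this stands, and it rules out several stronger readings that a reader might infer:

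- *That early risk cannot be told from late risk.* It can, in part: onset times are planned by arm.
- *That early risk is shown to be dose-related, or that the early peak applies to both event types.* The peak was seen in all treatment groups and concerns hemorrhage only.
- *That the arm order for bleeding reverses over time, as the diarrhea figures suggest* ("Between Weeks 8 and 16, this had decreased to 10.9% of the 400 mg QD arm and 15.3% of the 200 mg BID arm", after 54.3% and 40.6% in the first eight weeks). That is another toxicity, and 400 mg QD is not an arm here. The overall diarrhea comparison (65.7% against 48.1%) also agrees with the early one.
- *That Weeks 0–8 isolate the assigned dosage.* Holds, reductions and stops can occur at any time.
- *That the table was removed from an earlier SAP.* Nothing shows that one contained it.
- *That the analysis would have to be labelled post hoc.* SAP 1 says "If additional analyses are required to supplement the planned analyses described in this SAP, they will be identified as post hoc", but an analysis already specified in the protocol is not clearly an additional one. Its status is unclear.

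What does not stand is that the listing is equivalent. A listing of events counts only patients who had one. The form of the graph is unspecified, so it cannot be relied on to supply the number at risk. A separate duration table does not connect exposure to events.

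**Conclusion.** The point holds as a specific gap between protocol and SAP. The SAP leaves out, without explanation, a protocol-specified summary of two of the four primary safety components. As written it gives no by-arm incidence over patients at risk and no exposure-adjusted rate for them.

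The consequence is moderate. Onset timing remains visible, and no hypothesis test depends on the table. What is lost is a pre-specified comparison that takes account of who was still under observation. At equal underlying risk, 24 against 16 weeks of follow-up would change the crude percentage by a factor of about 1.4 to 1.5. That figure assumes a constant risk of 1% to 8% per interval and a complete difference in follow-up, so it marks an upper end rather than a forecast. The documents do not say how far follow-up will differ between arms, or in which direction.

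**What to change.** Add to SAP 13.1, for cardiac and for hemorrhage SMQ treatment-emergent events separately, a table by arm and 8-week interval (Weeks 0–8, 8–16, 16–24, then every 8 weeks while patients remain under observation):

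- **Numerator:** patients with a first event in the interval.
- **Denominator:** patients event-free at interval start and either still on treatment or within 30 days of the last dose.

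The 8-week interval, the SMQ grouping and the split by arm come from Protocol 11.6. The first-event rule and the denominator are a proposed specification, chosen to match the SAP's treatment-emergent window; the protocol does not state them. Present the table as descriptive. If the sponsor prefers not to produce it, the modification table should say so and give the reason.

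The cost is one SAP paragraph and one extra table from event and dosing dates already collected. The drawback is small, imprecise counts in later intervals, which the text should acknowledge so that differences between adjacent intervals are not over-read.

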2.1 Justification of Included Patient Population

MF is a serious, life-limiting condition with severe morbidity in advanced stages. Ruxolitinib is the only approved agent for treatment of MF. Patients who are intolerant or who have failed to maintain a robust response to ruxolitinib have no alternative therapies and are at high risk for early mortality.

Overview of Included Patient Population

Patients to be included in this study will have failed therapy with ruxolitinib on the basis of intolerance or lack of efficacy. This requirement is based on the unmet medical need in patients who failed to maintain benefit from the only approved agent. Intolerance is defined by a minimum of 28 days therapy with pre-defined safety issues as previously used in a phase 3 clinical study of a JAK inhibitor in MF patients (https://clinicaltrials.gov/ct2/show/NCT02101268). Suboptimal efficacy is defined based on consensus criteria and is based on a lack of spleen reduction and symptom improvement after 6 months of attempted treatment (Mesa et al 2016).

In addition, patients will be highly symptomatic (Dynamic International Prognostic Scoring System [DIPSS] risk score of Intermediate-1 to High Risk), and have splenomegaly as assessed by physical examination.

Patients must have had no recent cardiac or bleeding history, and meet cardiac and bleeding safety screening evaluations including electrocardiogram (ECG), echocardiogram and coagulation testing

results. Patients with baseline corrected QT interval (QTc) \geq 450 ms will be excluded from the study. Patients requiring concomitant medications with a significantly increased risk of QTc prolongation or bleeding will be excluded. Based on the observed limited increase in pacritinib concentration in the cytochrome P450 (CYP3A4) inhibitor interaction study with clarithromycin (Study PAC104), caution should be exercised when coadministering such inhibitors with pacritinib. For the PAC203 clinical study, patients requiring such inhibitors will be excluded (Appendix 5). Based on the substantive pacritinib concentration study with rifampin (Study PAC106), patients requiring such inducers (Appendix 6) will be excluded. Patients are also required to have adequate hepatic and renal organ function and the absence of known medical issues which might affect efficacy assessments, tolerability, or safety on study.

2.2 Independent Data Monitoring Committee

This study will utilize planned frequent monitoring by an IDMC. At a minimum, the IDMC will consist of 1 board-certified hematologist, 1 board-certified cardiologist, and 1 biostatistician experienced in adaptive design clinical studies. The role and responsibilities of the IDMC will be fully defined within the IDMC charter, including, but not limited to:

- Review safety data across arms, focusing on bleeding events, cardiac events, and deaths
- Evaluate cumulative safety as described in Section 11
- Make independent recommendations to the Sponsor on study continuation (continue without modification, continue with modification, or terminate) and on patient enrollment (hold or stop enrollment, enroll additional patients, close arm) as described in Section 11.
- Make independent recommendation to the Sponsor on pacritinib dose or dosages for further study

The IDMC charter will be written in collaboration between the Sponsor and members of the IDMC. In keeping with the terms of the charter, each IDMC meeting will have an open and closed session.

The first IDMC meeting for safety review is planned tooccur once 18 patients have been randomized and treated for 12 weeks and will meet approximately quarterly thereafter. Meeting minutes will be generated from each meeting and provided to the FDA within 10 business days of the meeting conclusion.

In addition to the IDMC, there will be an Independent Adjudication Committee (IAC) that will review all grade 4 or 5 cardiac and bleeding events to assess the principal condition that resulted in the outcome. The IAC will provide their assessment to the IDMC. Additional details on the IAC will be provided in the IAC charter.

2.3 Study Objectives

2.3.1 Primary Objective

The primary objective is to determine a recommended dosage of pacritinib for further clinical studies.

2.3.2 Secondary Objectives

The secondary objectives are as follows:

- 1. To examine the dose–response relationship for efficacy, as measured by spleen volume reduction (SVR) using MRI (preferred) or CT and TSS using the Myeloproliferative Neoplasm Symptom Assessment Form Total Symptom Score version 2.0 (MPN-SAF TSS 2.0)
- 2. To examine the dose-response relationship for safety with a focus on AEs of interest
- 3. To further characterize the pharmacokinetics (PK) and pharmacodynamics (PD) of pacritinib

3 Study Design

This is a dose-finding study in patients with PMF, PPV-MF, and PET-MF (DIPSS risk score of Intermediate-1 to High-Risk), who were previously treated with ruxolitinib. The study is designed to support a pacritinib dosage selection decision. Three dosages will be evaluated, with patients randomized 1:1:1 to pacritinib 100 mg OD, pacritinib 100 mg BID, or pacritinib 200 mg BID. Randomization will be stratified by baseline platelet count ($\leq 50,000/\mu$ L; >50,000/ μ L and $\leq 100,000/\mu$ L; and >100,000/ μ L). The most recent platelet count obtained prior to start of treatment will be the basis of stratification by baseline platelet count. Assigned treatment will continue until the patient experiences progressive disease, intolerable AEs, or withdraws consent, or until the assigned treatment arm is closed. No study treatment crossover will be allowed. All patients should complete all visit procedures through Week 24, including patients who stop pacritinib treatment or have protocol-defined progressive disease prior to Week 24, unless patient withdraws consent, dies, undergoes splenic irradiation or splenectomy, or initiates any nonprotocol-directed anti-myelofibrosis treatment. Following regulatory, Ethics or Institution Review Board approval of Amendment 6, study treatment for patients at and beyond the week-24 timepoint will terminate. Study assessments will cease following the End-of-Treatment or 30-day post (EOT) visit, as applicable. Patients who are benefiting from therapy as of study treatment termination may be allowed to continue receiving pacritinib under single patient expanded access or named patient programs at the investigator's discretion and subject to regulatory and Ethics or IRB approval.

The dosage selection process will be based on efficacy and safety parameters, including model-based dose response as described in Section 3.1.

An IDMC consisting of subject matter experts will be convened and chartered to perform an assessment of safety throughout the study. See Section 2.2 for additional information.

The following criteria (non-binding) have been established to guide the decision:

- In the event of the occurrence of 2 treatment-emergent CTCAE grade ≥4 cardiac AEs or 2 treatment-emergent CTCAE grade ≥4 hemorrhage AEs in the same treatment arm, suspend study enrollment and the IDMC will be convened to review the events including the IAC's assessment of the events. If the IDMC confirms the nature and grade of the events together with a relationship to study drug, the IDMC may recommend closure of one or more treatment arms. In the event one or more arms are suspended or terminated for a safety observation, randomization into the arm(s) will be halted immediately, however patients who are experiencing benefit, in the opinion of the investigator and Sponsor, and who were randomized to an arm that is suspended or terminated, may continue treatment.
- The FDA and other Competent Authorities will be notified of any IDMC meeting that is convened under these circumstances, and the resultant decision will be reported to the FDA within 2 business days. The MHRA will be informed via a substantial amendment.
- If closure of an arm occurs, patients will continue to be enrolled into each of the remaining treatment arms.

The determination of dose or dosages of pacritinib for further study will be based on efficacy, safety, dose–response, and PK/PD exposure–response relationship data after all enrolled patients reach Week 24 (or discontinue the study). Approximately 150 patients total or up to 50 patients per arm may be enrolled.

Spleen volume will be measured by MRI (preferred) or CT at baseline and Weeks 12 and 24 (Table 1). Patient-reported disease-related symptoms as assessed by the validated PRO instrument MPN-SAF TSS 2.0 will be collected daily using an electronic diary and evaluated as part of the dose–response relationship. DNA samples will also be collected for analysis of mutations associated with myelofibrosis at baseline and Week 24.

Safety will be monitored with physical examinations, clinical laboratory assessments (including hematologic, chemistry, and coagulation testing), and cardiac monitoring (including ECG and echocardiogram testing); specified study treatment dosage modifications will be followed to address identified abnormalities. Adverse event data will be collected throughout the study.

The Sponsor will collect PK samples from patients in each dosing arm at the following timepoints:

- Sparse Sampling (all patients): End of Week 12 and End of Week 24: 30 minutes to 0 hours (predose), 4 hours (± 10 minutes), and 8 hours (± 15 minutes) postdose
- Dense Sampling (performed at selected sites for approximately 6 to 8 patients total per dose arm, at which point all further patients will have PK evaluated by sparse sample collection): Week 1 Day 1: 2 hours (± 5 minutes), 4 hours (± 10 minutes), 6 hours (± 15 minutes), and 8 hours (± 15 minutes) postdose and 24 hours postdose (within 30 minutes before the Day 2 dose), End of Week 12 and End of Week 24: 30 minutes to 0 hours (predose), 2 hours (± 5 minutes), 4 hours (± 10 minutes), 6 hours (± 15 minutes), 4 hours

The PK parameters, minimum concentration observed (C_{min}), maximum concentration observed (C_{max}), and area under the curve (AUC) will be determined and summarized using descriptive statistics for each pacritinib dosage arm. Exposure-response analyses will be conducted on both safety and efficacy populations in the study. PD samples will be analyzed for biomarkers associated with the JAK/STAT pathway.

